12.5 Safety Committee(s)

12.5.1 Internal Novo Nordisk Safety Committee

Novo Nordisk will constitute an internal safety committee to perform ongoing safety surveillance of N8. The safety committee works according to a written guideline and will meet regularly to discuss and evaluate the overall safety for N8 for this trial and all other N8 trials. The Novo Nordisk safety committee can take action with regard to the patient safety for the trial based upon observations of the overall information for N8. Pre-defined rules for setting the enrolment on hold is described in Section [12.5.2](#).

The safety committee might meet to evaluate data at any time point during the conduct of the trial if deemed necessary.

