- Ethnicity (White, Asian, African, Other)
- Family history of inhibitors (Negative, Positive)
- FVIII gene mutation type (Low risk (small deletions/insertions of < 200 base pairs, missense mutations, and other including ~~splice~~ *splice* or promoter mutations), High risk (large deletions of over 200 base pairs, nonsense mutations, intron 22 or ~~one~~ *one* 1 inversions))

2.40 18.2.4 Supportive Secondary Endpoints

~~Outcome of inhibitor treatment will be listed and summarised.~~

2.41 18.3 Interim analysis

~~An interim analysis is planned to occur after the first 50 patients each have 50 ED. The interim analysis will include a full report of all data for the 50 patient until the cut-off date, which is the date the 50th patient had his exposure number 50.~~

~~The interim analysis is performed to file a marketing authorisation variation application to include PUP in the N8 label.~~

~~Furthermore, the interim will include a safety analysis for all patients exposed before the cut-off date. The safety analysis will include a Kaplan Meyer plot presenting the time to high titre inhibitor, clinically relevant inhibitor and inhibitor (≥ 0.6 BU/mL), respectively. All AEs, SAEs, MESIs and other abnormal safety parameters such as laboratory parameters and physical~~

examinations will be presented for all patients.

2.42 18.4 Sequential Safety Analysis/Safety Monitoring

There ~~are two~~ is one pre-planned safety interim analysis. At ~~each~~ this interim all patients exposed at the pre-defined time point, determined by number of patients exposed, will be evaluated for inhibitor development.

- Safety interim 1: After the first 25 patients have been to Visit 4 (20-25 exposure days)
- ~~Safety interim 2: After the first 50 patients have been to Visit 5 (50-55 exposure days)~~

The expected rate of inhibitors is 30–35% in previously untreated patients with severe haemophilia A.

The rules for putting the enrolment on hold are as follows;

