Inhibitor formation in 12 or more of all exposed patients at ~~the safety interim 1, or 22 or more of all exposed patients at interim 2,~~ will result in the ~~N8~~ *turoctocog alfa* safety committee evaluation of all cases of inhibitor formation. During these evaluations, ongoing treatment in the trial will continue, however new patients will not be enroled in the trial. The evaluation will provide the basis for a decision on any actions required for the trial to allow for continuation of enrolment or decision to terminate the trial.

2.43 18.7 Health Economics and Patient Reported Outcomes

Health economic data will be collected in the eCRF in connection with severe bleeds. Patient reported outcomes will be collected using questionnaires at visits 1, 3, and 75. The health economic and PRO data will be summarised using descriptive statistics.

2.44 27 References

Committee for medicinal products for human use (CHMP), Guideline on the Clinical Investigation of Recombinant and Human Plasma-derived Factor VIII Products, (EMEA/CHMP/BPWP/144533/2009). 2009 2011.

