5. To ensure a possibility of exploratory analysis in the future on remaining blood samples and to align with other PUP trials in haemophilia
6. To ensure timely interim analysis independent of number of inhibitor patients
7. The gap from once weekly to 3 times weekly infusion of preventive treatment was to big so sites have requested twice weekly frequency to avoid overdosing of patients
8. To ensure the number of planned recruited patients are fulfilled the number of sites are increased
9. 12 weeks between monitoring visits even if there are no patients at site have been reintroduced to ensure a check of trial supplies at site and thus possibility to enrol patients
10. To align with other guardian protocols and Global Safeties current definition of disease related bleedings
11. Ensure no misunderstanding regarding treatment requiring bleeds must be treated with trial product (turoctocog alfa)
12. Sites have requested a guideline for treatment of bleeding episodes
13. Align with current processes for publication of results
14. To guide sites if dosing during ITI treatment
15. Align flow chart with text in protocol
16. Enhance quality of protocol

Subject information/Informed consent:

17. Minimum mandatory safety text has been updated
18. Enhance quality of SI/IC

In this protocol amendment:

- Any new text is written ***in italics***.
- Any text deleted from the protocol is written using **strike through**.

2 Changes

1 Summary

....

Primary Endpoint:

Incidence rate of FVIII inhibitors (≥ 0.6 BU/ml) will be evaluated for the main phase of the trial

Key Secondary Endpoints:

....

Incidence rate of FVIII inhibitors (≥ 0.6 BU)

Key Inclusion Criteria:

....

- No prior use of purified clotting factor FVIII products (previous exposure, equal to or less than 5 ED to blood components, e.g. cryoprecipitate, fresh frozen plasma is accepted) *including commercially available NovoEight®/Novoeight®*

Trial Product

....

~~The dose for treatment of bleeds is decided by the Investigator but should be approximately 25-50 IU/kg in accordance with Guidelines for the Management of Haemophilia[†]. The maximum total daily dose of ruroctocog alfa for the treatment of bleeds is 200 IU/kg with a maximum dose per infusion of 100 IU/kg.~~

2 Flow chart

Table 2-1 Visit Flow Chart main trial phase

Visit number	Screen. Visit 1	Visit 2 [#]	Visit 3	Visit 4	Visit 5	Unscheduled Visit
Visit window	NA	≤ 21 d post V1	10 th - 15 th ED	20 th -25 th ED	50 th -55 th ED	

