12.5.2 Rules for putting the enrolment on hold

There is one pre-planned safety interim analysis. At this interim all patients exposed at the pre-defined time points determined by number of patients exposed will be evaluated for inhibitor development.

- Safety interim: After the first 25 patients *either* have been to Visit 4 (20-25 exposure days) *or have developed inhibitors before visit 4*

.....

The diagnosis of inhibitor is made if the patient has been tested positive for inhibitors ($BU \geq 0.6$ BU/mL) at two consecutive tests at central laboratory, sampled preferably within 2 weeks.

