18.3 Sequential Safety Analysis/Safety Monitoring

- Safety interim: After the first 25 patients *either* have been to Visit 4 (20-25 exposure days) *or have developed inhibitors before visit 4*

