12.1 Definitions

...

Serious Adverse Event (SAE):

A SAE is an experience that at any dose results in any of the following:

- Death
- A life-threatening experience ^{a)}
- In-patient hospitalisation or prolongation of existing hospitalisation ^{b)}
- A persistent or significant disability/incapacity ^{c)}
- A congenital anomaly/birth defectImportant medical events that may not result in death, be life-threatening ^{a)} or require hospitalisation^{b)} may be considered a SAE when, based upon appropriate medical judgement, they may jeopardise the patient and may require medical or surgical intervention to prevent one of the outcomes listed in this definition of SAE^{d)}. Suspicion of transmission of infectious agents via trial product and/or formation of inhibitory antibodies must always be considered an SAE

...

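### The 12-case enrolment hold is read only at the 25-patient interim, although a 12th confirmed inhibitor settles its outcome earlier: a cheap improvement, not an error in the limit

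*Combined protocol and SAP*

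**What the plan says.** Protocol Section 12.5.2, repeated in Section 18.3 (numbered 18.4 in version 1.0 and Amendment 1), plans one safety interim. A second look was removed by Amendment 1.

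- **Timing, as later amended:** "Safety interim: After the first 25 patients" have either reached Visit 4 (20–25 exposure days) "or have developed inhibitors before visit 4".
- **Limit:** "Inhibitor formation in 12 or more of all exposed patients at" this interim. A case needs two consecutive positive central-laboratory tests.
- **Consequence:** the internal safety committee evaluates all cases. Meanwhile no new patient is enrolled and ongoing treatment continues. The evaluation is the basis for deciding on any action needed "to allow for continuation of enrolment or decision to terminate the trial".
- **Expected rate:** "The expected rate of inhibitors is 30–35% in previously untreated patients with severe haemophilia A".

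Two neighbouring provisions matter. Under Section 12.5.1 the committee meets regularly, may meet at other times, and "can take action with regard to the patient safety for the trial". It works to a written guideline that is not in the documents. Section 20 says that the cases are evaluated, with enrolment paused, if the limit is reached. It names no date, but the sentence follows directly on the one about the planned interim analysis and sends the reader to the monitoring section for the rule.

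**The concern.** The limit is a bare count of confirmed cases. It has no denominator, and nothing in the documents removes a confirmed case from it. Once the 12th case is confirmed, the interim can only give one answer, so waiting for it adds nothing on whether the limit is met. By default, Sections 12.5.2 and 18.3 let previously untreated children under 6 years keep starting until the interim arrives. At stake are the children who start after the trial's own limit has been met but before the evaluation that the limit is meant to trigger.

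**Working it through.** **1. Figure to reproduce.** The plan states no error rate or derivation for the limit. As a proportion of 25 it is 12/25 = 48%.

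**2. Probability of crossing at 25 patients.** With X binomial(25, p), P(X ≥ 12) = Σ C(25, x) p^x (1−p)^(25−x) for x = 12 to 25. The rates 30% and 35% are the plan's; 50% and 60% are assumed, to represent a worse product.

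**3. Same limit read after every patient.** The 12th case falls at patient k with probability C(k−1, 11) p^12 (1−p)^(k−12), for k = 12 to 25. The sum equals step 2 at every rate, as it must for a count that cannot fall. Only the timing differs.

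| True rate | P(cross), either reading | P(12th case before patient 25) | Share of crossings | Mean k | Patients left (25 − k) |
|---|---|---|---|---|---|
| 30% | 0.0442 | 0.0314 | 71% | 23.06 | 1.94 |
| 35% | 0.1254 | 0.0942 | 75% | 22.74 | 2.26 |
| 50% | 0.6550 | 0.5806 | 89% | 21.16 | 3.84 |
| 60% | 0.9222 | 0.8857 | 96% | 19.34 | 5.66 |

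**4. Children started in the window.** This needs calendar time, which the plan fixes only in part. The simulation ran 30,000 trials in each of 32 settings per rate.

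- Accrual: up to 60 patients, exponential arrivals, at 60/45 = 1.33 per month (45 months is stated in Section 7 as amended) or 60/53 = 1.13 per month (53 months from that section's dates, December 2011 to Q2 2016).
- Visit 4: uniform over 3–9 months (assumed), or over 1.2–12 months, from 20/50 × 3 and 25/50 × 24 using the stated 3–24 months to 50 exposure days.
- Assumed: 100% or 75% of inhibitors arise before Visit 4; dropout 0 or 15%; detection continuous or only at Visits 3, 4 and 5; half a month to confirm.
- T25 is when the 25th patient reaches Visit 4 or has a confirmed inhibitor. T12 is the 12th confirmed case among all exposed patients. Children counted are those starting in (T12, T25], given T12 ≤ T25.

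Ranges are the minimum and maximum over the 32 settings:

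| True rate | P(cross), all exposed counted | Mean children, given crossing | Mean wait (months) | Crossings with no start in the window | Mean children over all trials |
|---|---|---|---|---|---|
| 30% | 2–9% | 2.0–2.9 | 1.6–2.5 | 32–44% | 0.03–0.2 |
| 35% | 5–21% | 2.3–3.3 | 1.7–2.9 | 29–38% | 0.1–0.6 |
| 50% | 39–77% | 3.2–5.4 | 2.4–4.7 | 16–25% | 1.2–4.1 |
| 60% | 71–96% | 4.2–7.8 | 3.2–6.7 | 6–17% | 3.0–7.4 |

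**5. Excess inhibitors per crossing.** Children × (true rate − 0.30 or 0.35), taking 30–35% as the rate on another product. At 30%: −0.14 to 0. At 35%: 0 to 0.17. At 50%: 3.2 × 0.15 = 0.5 to 5.4 × 0.20 = 1.1. At 60%: 4.2 × 0.25 = 1.1 to 7.8 × 0.30 = 2.3.

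**6. If enrolment resumes.** After a hold of 1 to 3 months, the earlier reading only postpones starts: 0.7–2.3 at 30–35%, 0.9–3.0 at 50%, 1.0–3.6 at 60%.

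**The case against.** The strongest reply is that the gap is largely covered elsewhere. The trial is open-label, the committee may meet at any time, and Section 12.1 as amended says that "formation of inhibitory antibodies must always be considered an SAE", with the AE form due within 24 hours. The sponsor may stop the trial or part of it at any time. Harm therefore needs a committee that sees 12 confirmed inhibitors and does nothing until the interim. This stands as a reason why the practical effect is probably smaller than the figures above. It does not close the gap, because the power is discretionary and no count goes with it in the available text. The committee's written guideline might contain a running trigger; that cannot be known from the documents.

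Section 20 could be read as an immediate trigger. Its context is the planned interim, and neither 12.5.2 nor 18.3 says so.

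The sponsor has already shortened the wait by counting inhibitor patients among the 25, with the reason "To ensure timely interim analysis independent of number of inhibitor patients". That helps but does not remove the wait.

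It is also fair that one planned look plus discretionary surveillance is a legitimate design, that rates of 50–60% appear nowhere in the documents, and that the calculation treats arrival as first dose. First dosing may come after enrolment, and a hold on enrolment does not clearly stop children already enrolled but undosed.

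A reader might also infer that Section 20 points to a wrong section number. The documents do not support that. The reference to 18.4 stands in version 1.0, where that number was correct, and Amendment 7 later changed Section 20 to one interim. The current cross-reference is not shown.

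**Conclusion.** The point holds as a cheap improvement to the timing of the hold. A reader might infer that the limit of 12 is wrong, or that the plan prevents action before the interim. Neither follows: nothing here bears on the choice of 12, and Section 12.5.1 allows earlier action.

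If the limit is crossed and the committee does not act earlier, about 2–3 children on average start in the window at a true 30–35%, and about 3–8 at an assumed 50–60%. These are upper bounds on starts avoided: they need a hold lasting until the interim would have occurred, or termination. They are not counts of inhibitors avoided. At the expected rate crossing is uncommon, the average over all trials is at most 0.6 children, and the expected excess of inhibitors is about zero. The benefit lies in the case of a product worse than expected, which is the case the rule exists for. The sizes rest on the assumed accrual, Visit 4 timing and detection pattern; the equal probability of a hold rests on logic alone.

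**What to change.** In Sections 12.5.2 and 18.3, add wording such as:

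*When the 12th inhibitor confirmed by two consecutive positive central-laboratory tests is recorded, at or before the planned safety interim, new enrolment is held and the safety committee evaluation of all cases starts. The evaluation shows the number of patients exposed at that date and their exposure days. If the 12th case has not been recorded by then, the interim takes place as now.*

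The existing text on the conduct and outcome of the evaluation stays. The restriction to the period up to the interim is essential. Without it, 12 cases among 50 patients would be reached with probability 0.861 at a true 30% and 0.966 at 35%, so the hold would trigger in most trials at the expected rate.

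**Cost:** the same short text in two sections and a running count of centrally confirmed cases. Raw SAE and MESI reports will not do, because a first positive test is reportable even if the second is negative. The review comes earlier, with fewer than 25 patients of resolved early status (simulated mean 22–23 at 30–35%, 20–22 at 50%, 18–21 at 60%), in a group enriched for early cases. Showing the number exposed and their exposure days lets the committee allow for this.

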2.45 Appendix B Whole Blood Volume Rules in the Paediatric Population

The blood volume collected from the subject for all tests should not exceed 1% of the whole blood volume at any single time and 3% of whole blood volume in 28 days. This requirement is in line with European regulatory requirements (Directive 2001/20/EC) and FDA requirements. The table below shows the estimated blood volume in children weighing from 6-25 kg and the blood volume that can be taken at any single time and in 28 days according to European regulatory requirements (Directive 2001/20/EC) and FDA requirements.

Total Blood volume according to Geigy Scientific Table

Children 1-5 years of age

Weight (kg)	Blood volume (ml/kg)	Total Blood volume (ml)	Volume/blood sample (1%)	Volume /28 days (3%)
6	80	480	4,8	14,4
7	80	560	5,6	16,80
8	80	640	6,4	19,2
9	80	720	7,2	21,3
10	80	800	8,0	24,0
11	80	880	8,8	26,4
12	80	960	9,6	28,8
13	80	1040	10,4	31,2
14	80	1120	11,2	33,6
15	80	1200	12,0	36,0
16	80	1280	12,8	38,4
17	80	1360	13,6	40,8

Weight (kg)	Blood volume (ml/kg)	Total Blood volume (ml)	Volume/blood sample (1%)	Volume /28 days (3%)
18	80	1440	14.4	43.2
19	80	1520	15.2	45.6
20	80	1600	16.0	48.0
21	80	1680	16.8	50.4
22	80	1760	17.6	52.8
23	80	1840	18.4	55.2
24	80	1920	19.2	57.6
25	80	2000	20.0	60.0

Substantial Protocol Amendment no. 2
to Protocol, final version 2.0 dated 01 February 2012

Trial ID: NN7008-3809

guardian™⁴

**Safety and Efficacy of NNC 0155-0000-0004 in
Prevention and Treatment of Bleeds in Paediatric
Previously Untreated Patients with Haemophilia A**

Trial phase: 3

Applicable to Russia

Amendment originator:

[REDACTED]

[REDACTED]

This ~~confidential~~ document is the property of Novo Nordisk. ~~No unpublished information contained herein may be disclosed without prior written approval from Novo Nordisk. Access to this document must be restricted to relevant parties.~~

Table of Contents

	Page
Table of Contents	2
1 Introduction including Rationale for the Substantial Protocol Amendment.....	3
2 Changes to the protocol	4

1 Introduction including Rationale for the Substantial Protocol Amendment

The reason for this substantial protocol amendment is to change the Laboratory where CD4⁺ T-cell count will be performed for investigator sites in Russia. CD4⁺ T-cell count will be performed in the central laboratory.

In this substantial protocol amendment

- Any new text is written in *italic*.
- Any text deleted from the protocol is written with a ~~strike through~~.

2 Changes to the protocol

8 Methods and Assessments

...

8.2.7.2 Local Laboratory Tests

Assessments of haematology, FVIII trough levels and ~~CD4⁺ T-cell count (if applicable)~~ will be done at the local laboratory as per standard of practice at the participating site. Laboratory results from the local laboratory will be recorded in the eCRF.

Table 2–1 Visit Flow Chart main trial phase	6
Table 2–2 Visit Flow Chart trial extension phase	7

1 Introduction including rationale for the substantial protocol amendment

This global substantial amendment has been prepared to:

- change the treatment after end of trial
- introduce the concept of two different phases of the trial, a main phase and an extension phase
- present the results from previous trials in the guardian™ clinical programme
- extend the trial duration
- make it optional to conduct a phone “visit” for severe bleedings.

The current clinical trial, guardian™ 4 (NN7008-3809), includes Previously Untreated Patients (PUP), treated with turoctocog alfa for at least 50 exposure days (ED). To preserve the homogeneity of the patient cohort, patients will not be transferred to guardian™ 2 (NN7008-3568), which holds a trial population consisting of Previously Treated Patients (PTP) > 100 ED.

In this substantial protocol amendment:

- Any new text is written in ***italics***.
- Any text deleted from the protocol is written using ~~strike through~~.

The below changes will not be disclosed in the following sections due to they are minor changes that do not affect the content of the text;

- minor inconsistencies and ambiguities, and typographical errors.

2 Changes

2.1 1 Summary

Objectives and Endpoints

Primary Endpoint:

- Incidence rate of FVIII inhibitors (≥ 0.6 BU/mL) will be evaluated *for the main phase of the trial from Visit 2 to End of Trial (EoT) Visit/Visit 5*

Key Secondary Endpoints:

The secondary endpoints will be evaluated for the main phase of trial, for the extension phase of trial, and for the combined main and extension phases.

- Haemostatic effect of NNC 0155-0000-0004 on treatment of bleeds assessed on a predefined four point scale: Excellent, Good, Moderate and None ~~will be evaluated from Visit 2 to EoT Visit/Visit 5~~
- Annualized bleeding rate ~~will be evaluated from Visit 2 to EoT Visit/Visit 5~~
- *Incidence rate of FVIII inhibitors (≥ 0.6 BU/mL)*

Trial Design

The trial consists of two phases. In the main phase The an aggregated number of at least 50 patients will receive preventive treatment with NNC 0155-0000-0004 until they reach a minimum of 50 exposure days² (ED) or until they develop inhibitors. After that the patient will continue in the extension phase, which will last for approximately 3.5 years. The patients will stay in the trial for approximately 3-24 months, and The estimated total duration of the trial is approximately 50 months years.

~~The trial is designed in accordance with European Medicines Agency (EMA) guideline on the Clinical Investigation of Recombinant and Human Plasma-Derived Factor VIII Products⁴.~~

2.2 2 Flow Chart

(Clarification note: For Table 2-1 only information that are subjected to changes are presented.)

Table 2-1 Visit Flow Chart *main trial phase*

Visit number	Screen. Visit 1	Visit 2	Visit 3	Visit 4	Visit 5	Unscheduled Visit
Visit window	NA	14 ± 7 d post V1	10 th -15 th ED	20 th -25 th ED	50 th - 55 th ED	
FVIII trough level			•b	•b	•b	
FVIII recovery		•b	•b	•b	•b	•b,c
T cells subset: CD4+	•b,h	•b,h				•b,h
turoctocog alfa administration		•b	•b	•b	•b	•b
Diary and Trial card dispensing and/or collection	•e	•e	•e	•e	•e	•b
Completion session in IV/WRS					—	
Drug dispensing and accountability		•g	•	•	•g	•b
End of trial form					•	

Table 2-2 presents the rolling visit schedule in the extension phase over the period of one year. It comes to effect after Visit 5 or after ITI treatment.

Table 2–2 Visit Flow Chart trial extension phase

Visit type	Dispensing		Assessment& Dispensing		Dispensing		Assessment& Dispensing		End of Trial	Unsch Visit
Visit number[#]	6		7		8		9		10	11
Previous visit time(w)	-8		-8		-10		-8		-8	< 8
Visit window	± 1w		± 1w		± 1w		± 1w		NA	NA
ASSESSMENTS										
Withdrawal Criteria	•	•	•	•	•	•	•	•	•	•
Concomitant medication	•	•	•	•	•	•	•	•	•	•b
Body measurements			•c				•c		•	
EFFICACY										
Bleed(s)	•b	•b	•b	•b	•b	•b	•b	•b	•b	•b
SAFETY										
Adverse events	•	•	•	•	•	•	•	•	•	•b
Physical examination			•a				•a		•	
Vital signs			•a				•a		•	
FVIII inhibitors	•a	•a	•	•a	•a	•	•	•	•	•a
FVIII trough level			•a				•a			
FVIII recovery	•a	•a	•a	•a	•a	•a	•a	•a	•a	
Biochemistry & Haematology			•				•		•	•a
OTHER ASSESSMENTS										
PRO questionnaire							•		•	
HE assessment	•b	•b	•b	•b	•b	•b	•b	•b	•b	•b
Viral antibody test (if HIV, HBsAg and/or HCV status unknown)									•	•b
T cells subset: CD4+										•b
TRIAL MATERIAL										
turoctocog alfa administration	•a	•a	•a	•a	•a	•a	•a	•a	•	
Diary card dispensing and/or collection	•	•	•	•	•	•	•	•	•d	•a
Review of patient diary and entry of data in eCRF	•	•	•	•	•	•	•	•	•	•a
Completion session in IV/WRS									•	
Drug dispensing and accountability	•	•	•	•	•	•	•	•	•e	•a
EoT form									•	

- Presented numbers are for the first 12 months. Visit numbers for future years will be in consecutive order

a – Optional, at discretion of investigator

b – If applicable

c – Weight only
d – Collection only
e – Accountability only

[figure not shown]
[figure not shown]

Figure 2-1 Trial Design

~~75 patients are planned to be screened to get approximately 60 enroled, and 50 completers. Screening will be done at Visit 1, 14 ± 7 days prior to Visit 2. At Visit 2 eligible patients are enroled and preventive treatment with investigational product (turoctocog alfa) starts if applicable at Visit 2 (may start after the first two bleeds), see Section 5.3 and is completed at V5. At visit 5, after ≥ 50 ED, patients will leave the main phase of the trial and continue in the extension~~

phase. Patients who develop inhibitors can continue with ITI treatment with an alternative visit schedule (down ward arrows). If ITI treatment is successful these patients can continue with preventive treatment according to the extension phase (upward arrows). The patients will belong to either of the groups main-phase, extension phase or inhibitor cohort.

2.3 3.1.1.1 Pre-Clinical and Clinical Data

Two phase 3 trials were completed in 2011, i.e. the pivotal trial guardian™ 1 (NN7008-3543) and the paediatric trial guardian™ 3 (NN7008-3545) in PTP with severe haemophilia A (FVIII \leq 1%). In both trials, the primary objective was to assess safety, including the incidence rate of FVIII inhibitors (\geq 0.6 BU).

A total of 150 male patients aged 12 to 60 years were dosed in the guardian™ 1 trial, whereof 148 patients had at least 50 ED and 142 patients had at least 75 preventive ED in the trial. No clinically significant safety issues were identified and no FVIII inhibitors were detected. The success rate for treatment of bleeds was 84.5% (excluding bleeds for which there was no outcome reported).

A total of 63 male patients below 12 years of age were dosed in guardian™ 3 whereof 59 patients (28 children [0– $<$ 6 years] and 31 children [6– $<$ 12 years]) had at least 50 ED in the trial. No clinically significant safety issues were identified and no FVIII inhibitors were detected. The success rate for treatment of bleeds was 94.3% (excluding bleeds for which there was no outcome reported).

Further PK data have been obtained in the NN7008-3600 trial with six Japanese patients and in the NN7008-3893 trial with four additional adult patients. Both these trials used two different lots of drug product. In the NN7008-3600 trial, the PK properties of a single dose of turoctocog alfa in the Japanese population of patients with severe haemophilia A were successfully characterised. In the NN7008-3893 trial, three of the patients were of Asian and 1 was of Caucasian racial origin, and all patients completed the trial. No safety concerns were observed.

After completing the guardian™ 1 and guardian™ 3 trials, 189 of the 206 completing patients have continued treatment with turoctocog alfa within the extension trial guardian™ 2 (NN7008-3568), and the total clinical experience as of Nov 21 2011 exceeds 30000 ED. Despite regular monitoring and testing, no safety concerns have yet been detected and no patient has developed a FVIII inhibitor within the trials.

Recently two major clinical trials were completed in the Novo Nordisk turoctocog alfa development program, the pivotal phase 3 trial (guardian™ 1/NN7008-3543), the paediatric trial (guardian™ 3/NN7008-3545), and another large study is on-going, the extension trial

~~(guardian™ 2/NN7008-3568). The accumulated clinical experience with turoctocog alfa is now approaching 30000 exposure days (ED).~~

2.4 3.1.1.2 Risks and Benefits

~~After completing the present trial (guardian™ 4), eligible patients will be offered to continue with turoctocog alfa in an extension the trial until product launch or until the end of trial, should market authorisation not be obtained, see Section 7.5.4 for details. This serves to minimise the patients' need of switching to other FVIII products.~~

2.5 3.2 Rationale for the Trial

~~The guardian™ 4 trial is a prospective clinical phase 3b trial intended at demonstrating safety and efficacy of turoctocog alfa in PUP < 6 years of age with severe haemophilia A. The trial will continue until at least 50 patients have received at least 50 ED to turoctocog alfa.~~

2.6 4.2 Endpoint(s)

Primary Endpoint

- Incidence rate of FVIII inhibitors (≥ 0.6 BU/mL) will be evaluated for the main phase of the trial

Secondary Endpoint(s)

The secondary endpoints will be evaluated for the main phase of trial, for the extension phase of trial, and for the combined main and extension phases..

Safety Endpoints:

- ---
- Incidence rate of FVIII inhibitors (≥ 0.6 BU/mL).

2.7 5.1 Type of Trial

The trial comprises 5 planned visits consists of two phases i.e. main and extension, respectively. In the main phase the patients will attend a screening visit (Visit 1) in order to assess their eligibility. At Visit 2 eligible patient will receive their first dose, if applicable, and will be scheduled to attend for 3 more visits. After Visit 5 the patients will enter the extension phase, and a rolling visit schedule will apply with 6 planned visits (including 4 dispensing visits) per year.

The *main trial phase will be completed when the aggregated number of patients will be scheduled to*, who have either received treatment with turoctocog alfa for at least 50 ED or developed inhibitors, are at least 50. ~~which~~ For the individual patient it translates into duration of the *main phase* of approximately 3-24 months depending on the dose regimens (and bleeding pattern). The duration of the extension phase may be up to 3.5 years, and the total duration of the trial is estimated to be approximately 50 months years, please see Section 7.

Patients who develop inhibitors during the trial may continue treatment with turoctocog alfa and will follow an alternative visit schedule, see Section 5.3.4. *These patients will be considered as a separate cohort and will be evaluated accordingly, please refer to Section 18.2.2.*

Details on the trial design can be found in Figure 2-1 and details on the individual visits can be found in Table 2-1 and 2-2, and in Section 8.

2.8 5.3 Treatment of Patients

Approximately 60 patients are expected to be enroled into the trial in order to have 50 *evaluable* patients ~~completing in the main phase of the trial~~ (estimated dropout rate is 15-20%). For replacement of withdrawn patients, please refer to Section 6.5.

The maximum duration of treatment of a patient from first to last turoctocog alfa administration is approximately 24-4 years month.

2.9 5.3.2 Treatment of Bleeds and Dose Adjustment

During preventive treatment, break-through bleeds may occur and require extra doses of turoctocog alfa. Treatment should be started as soon as a bleed is identified. *All bleeds, mild/moderate and severe, bleeds* can be treated at home. ~~whereas For severe bleeds (see Section 8.3.1.1) must always be evaluated by the Investigator should evaluate if the patient should be seen preferably at the clinic. However, even with severe bleeds treatment should be started immediately at home if possible.~~ All bleeds must be reported to the clinic within 24 hours from onset of the bleed.

2.10 5.3.4 Treatment of Patients with Inhibitors

Patients who develop inhibitors, within this trial, will be offered continued treatment with turoctocog alfa for 12 months. It may also be decided by the Investigator and/or parent/legal representative to withdraw the patient.

The ~~initiation~~, dose level and dosing frequency of inhibitor treatment will be decided by the Investigator based on clinical evaluation and local standards, and it should be documented in the eCRF. Within this trial, 'inhibitor treatment' includes Immune Tolerance Induction (ITI) as well as smaller dose adjustments with low responding and/or clinical insignificant inhibitors.

If needed and decided by the Investigator, the initiation of the inhibitor treatment with turoctocog alfa can be delayed for up to 6 months from the time of diagnosis of inhibitor.

If the inhibitor disappears (BU <0.6/mL) during the ITI treatment, the patient should resume preventive treatment as recommended in this protocol, see Table 5-1, following the visit schedule in the extension phase. For patients still with positive inhibitors after 12 months ITI treatment, continued trial participation will be evaluated based on the level of inhibitors. After completion of the inhibitor treatment, or if preventive treatment is resumed, the patient will be called to an End of trial Visit (Visit 5).

2.11 5.4 Treatment after End of Trial

It is expected that turoctocog alfa will be granted marketing authorisation and is commercially available when the patients complete this trial. ~~Where no marketing authorisation has been granted, eligible patients will be offered to continue in the phase 3b extension trial (guardianTM 2), see Section 3.2.1, as applicable by local regulation and rules.~~

2.12 6.1 Number of Patients to be studied

Countries planned to participate: Austria, Brazil, China, Croatia, ~~Czech Republic~~, Greece, Hong Kong, Japan, ~~Malaysia~~, Russia, ~~Serbia~~, Spain, Turkey, ~~UK~~ and US.

Planned number of patients to be screened (i.e. documented informed consent): 7565

2.13 6.4 Withdrawal Criteria

- ~~1. Haemostasis not achievable with turoctocog alfa: The bleed cannot be controlled after 48 hours using recommended doses of turoctocog alfa~~

Withdrawn patients should be scheduled for an EoT Visit (Visit 5) as soon as possible and within 28 days after the last turoctocog alfa administration, and preferably prior to initiation of treatment with another FVIII product. The Investigator should aim to conduct all procedures as specified in the protocol for the EoT Visit 5.

2.14 6.5 Patient Replacement

Withdrawn patients may be replaced to ensure that 50 patients complete the trial with at least 50 ED. Assuming a drop-out rate of 2015%, it is estimated that 60 patients must be enroled to obtain the 50 completed patients. This may, however, be adjusted during the trial based on the actual drop-out rate.

2.15 6.6 Rationale for Trial Population

Rational for Withdrawal Criteria:

- Criterion~~ona~~ nos. 1 is included to protect the patient's safety
- Criterion no. 23 is selected not to confound the effects of the investigational product.

2.16 7 Trial Schedule

Planned LPLV: **April QIII 2016**

The duration of the trial for the individual country is dependent upon the timelines of market authorisation and commercial availability of the trial product. Should market authorisation not be obtained, the maximum trial duration is approximately 5 years.

2.17 8.1.1 Overall Procedures, Assessments and Methods

Specific procedures, assessments and methods for the scheduled visits are described in the sections below, and the list of assessments for each visit is presented in the flow charts, see Table 2-1 and 2-2.

2.18 8.1.2 Visit 1, Screening Visit

For all patients with a signed Informed Consent Form (ICF), the Investigator will, through IV/WRS, assign a unique 6 digit patient number. The patient number is maintained throughout the trial and ~~continuously maintained should the patient be enroled in the extension trial, see Section 5.4.~~

2.19 8.1.4 Visit 3 to Visit 5

~~Visit 5 should also be completed for withdrawn patients.~~

2.20 8.1.5 Unscheduled Visit

The unscheduled visit can be performed after the enrolment into the trial until the EoT Visit (**Visit5**) as either telephone contact or a site visit. Unscheduled visits will also be performed during inhibitor treatment, see Section 8.1.5.2, and *for surgical* procedures, Section 8.1.5.1. Please find listed in Table 2–1 and Table 2–2 the assessments, which should be performed at an unscheduled visit. The date and time of the visit should be recorded in the eCRF.

2.21 8.1.5.2 Inhibitor Treatment Visit

—

The alternative visit schedule will remain as long as the patient is treated for inhibitor. When the last inhibitor treatment visit has been performed, the patient will be called to an End of Trial Visit (Visit 5).

2.22 8.1.6 *Extension phase Visits*

These are visits to be performed for patients, who have completed the main phase and after Visit 5 continue in the extension phase. Patients, who resume preventive treatment after completed ITI treatment, will also follow the visit schedule in the extension phase. The patients will be called to the visits according to a rolling visit schedule, which runs over one year. There are two kinds of visits, Dispensing (4) and Assessment&Dispensing (2), and the aggregated planned number of visits over one year is 6.

Please also see Table 2-2 for your reference.

2.23 8.1.7 *EoT Visit*

Within 8 weeks of the last scheduled visit in the extension phase the patient should be called to an EoT Visit. For patients, who discontinue the trial, an EoT visit should be performed within 28 days.

2.24 8.2.1 Adverse Events

Monitoring of Adverse Events will be performed from the first trial-related activity to the EoT Visit (Visit 5) and at potential follow-up visits, according to procedures described in Section 12.

2.25 8.2.2 FVIII Inhibitors

All patients will be examined regularly for the development of FVIII neutralising antibodies (inhibitors). The tests will be performed at Visit 1 and Visits 3-5 *in the main phase of the trial, and at the Assessment&Dispensing Visits in the extension phase, i.e. at least twice annually.*

2.26 8.2.3 FVIII Recovery

—

Samples for FVIII recovery will be sent to the central laboratory for analysis, *see Section 8.2.7.2.*

2.27 8.2.4 FVIII Trough Level Assessment

The Investigator can at his/her discretion perform trough level assessments at any time during the trial. ~~Visit 3-4~~

2.28 8.2.5 Haematology

